3.2 DRUG ADMINISTRATION

rhIL-15 will be given as a subcutaneous (s.c.) injection once daily Monday-Friday following premedication with acetaminophen (preferred) and/or ibuprofen (if reaction despite acetaminophen) as follows:

Version Date: 09/24/2021

• 0.5 mcg/kg/dose during weeks 1 and 2 for cohort 1

- 1.0 mcg/kg/dose during weeks 1 and 2 for cohort 2
- 2.0 mcg/kg/dose during weeks 1 and 2 for cohort 3

Patients will receive up to 10 doses of rhIL-15.

NOTE: Refer to **Appendix F** for calculating IL-15 doses. Included in this section is dose calculation for obese patients.

On Day 1 (or before if clinically indicated) of Week 3, patients will be admitted to the NIH Clinical Center inpatient unit for the alemtuzumab infusions. Patients may be discharged from the inpatient unit and treated in the outpatient clinic when their experience with the treatment indicates that the alemtuzumab can be given safely in an outpatient setting. On Day 1 of Week 3, all patients will receive a 3 mg dose of alemtuzumab with premedication (650 mg acetaminophen and 25-50 mg diphenhydramine). If the dose is tolerated without significant toxicity (\leq grade 2 acute, infusion related toxicity and grade 1 or less skin rash) the patient will receive a 10 mg dose on Day 2 of treatment with the same premedication. If this is well tolerated the dose on Day 3 and Day 5 should be 30 mg with the same premedication.

Alemtuzumab will be administered by intravenous (IV) infusion over a minimum of 2 hours and maximum of 12 hours.

NOTE: Refer to Section **14.2.5** Administration procedures: for more detailed instructions about alemtuzumab infusion times.

After patients have completed and tolerated their initiation dosing of alemtuzumab during week 3 of treatment, treatment will be continued on the t.i.w. schedule at 30 mg with premedication as defined above (650 mg acetaminophen and 25-50 mg diphenhydramine) during weeks 4, 5 and 6.

Insertion of percutaneously inserted central catheter (PICC) or other appropriate vascular access device is permitted.

Treatment may be given on inpatient or outpatient basis. Patients may be hospitalized at the NIH Clinical Center Hospital for convenience and/or social reasons. These hospitalizations will not be considered adverse events and therefore will not require expedited reporting to the IRB.

Patients with acute-subtype ATL deemed by the PI or treating investigator to be at high risk for CNS relapse who have not received CNS prophylaxis as part of their prior treatment may receive prophylaxis in the form of cytarabine 40 mg, methotrexate 15 mg, and hydrocortisone 50 mg administered intrathecally (IT) no earlier than Week 3 and every 6-8 weeks thereafter for up to three doses, and may be given on the same day as alemtuzumab. Cytarabine or methotrexate may be omitted in case of prior intolerance or toxicity attributed to either drug. Platelet counts of ≥70,000 /uL need to be confirmed prior to each administration. If CNS disease is detected by cytology or flow cytometry of cerebrospinal fluid taken during IT drug administration, this will be considered disease progression and the patient will be taken off study. These medications (commercial supplies) will be supplied by the Clinical Center with preparation and administration to follow standard clinical guidelines and requirements.

3.3 DOSE MODIFICATIONS

After patients have completed and tolerated their initiation dosing of alemtuzumab during week 3 of treatment, they will continue to receive the standard three times a week (t.i.w.) alemtuzumab dosing (30 mg Monday, Wednesday and Friday) for up to 13 doses in the absence of disease

Version Date: 09/24/2021

progression or unacceptable toxicity. In **Table 1** and **Table 2**, and **Figure 10** below describe alemtuzumab dose modifications for toxicities related to alemtuzumab.

Table 1: Dose Modification of Alemtuzumab for non-hematologic toxicity related to alemtuzumab

Grade	Occurrence	Dose	Immediate Action	Resumption of Therapy
1	Any	Any	None	No interruption
2	Any	Any	None	No interruption
3	1 st	30 mg	**Hold alemtuzumab until toxicity resolves to Grade ≤ 1 or baseline	Resume alemtuzumab at 10 mg tiw, increase to 30 mg tiw if and when no Grade ≤2 AEs
3	2 nd	30 mg	**Hold alemtuzumab until toxicity resolves to Grade ≤ 1 or baseline	Resume alemtuzumab at 10 mg tiw
3	1 st	10 mg	**Hold alemtuzumab until toxicity resolves to Grade ≤ 1 or baseline	Resume alemtuzumab at 10 mg tiw
3	2 nd	10 mg	Stop alemtuzumab	Stop alemtuzumab
3: allergic reaction	1 st	Any	Stop alemtuzumab	Stop alemtuzumab
3: infection	1 st	Any	**Hold alemtuzumab until antibiotics stopped	Resume alemtuzumab at 30 mg tiw
	2 nd	Any	**Hold alemtuzumab until antibiotics stopped	Resume alemtuzumab at 10 mg tiw
	3rd	Any	Stop alemtuzumab	Stop alemtuzumab
4	Any	Any	Stop alemtuzumab	Stop alemtuzumab

^{**}If alemtuzumab is held >7 days, restart at 3 mg dose and titrate up as in the first week.

Figure 10: Titration and dose modification of alemtuzumab for non-hematologic toxicity related to alemtuzumab

[figure not shown]

Table 2: Dose Modification of alemtuzumab for hematologic toxicity related to alemtuzumab

^{**}Patients with catheter infection or transient bacteremia may restart alemtuzumab sooner if they are clinically stable and surveillance blood cultures on antibiotic treatment are consistently negative.

Version Date: 09/24/2021

Grade	Occurrence	Immediate Action	Resumption of Therapy		
1	Any	None	No interruption		
2	Any	None	No interruption		
3	Any	None	No interruption		
4	1 st	**Hold therapy until toxicity resolves to Grade ≤ 1 or baseline	Resume alemtuzumab at 30 mg tiw		
4	2 nd	**Hold therapy until toxicity resolves to Grade ≤ 1 or baseline	Resume alemtuzumab at 10 mg tiw		
4	3 rd	Stop alemtuzumab	Stop alemtuzumab.		
Any grade autoimmune cytopenia	Any	Stop alemtuzumab	Stop alemtuzumab		
**If alemtuzumab is held >7 days, restart at 3 mg dose and titrate up as in the first week.					

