3.1.1 Dose-Limiting Toxicity for rhIL-15

There are some well-described, clinically inconsequential side effects associated with IL-15 immunotherapy that are addressed differently than with other types of cancer therapies and affect the consideration of DLTs. Patients receiving rh-cytokines often have an initial decrease in their total white blood cell (WBC) counts, significant lymphopenia and occasionally some degree of neutropenia early in the course of their treatment. Unlike cytopenias noted in patients receiving cytotoxic chemotherapies or alemtuzumab treatment, these drops are usually transient and presumed to be related to increased margination (adherence to blood vessel endothelium) or alterations in trafficking that reduces the number of circulating cells rather than the destruction of the mature effector and bone marrow precursor cells. As such, rh-cytokine treatment resulting in grade 3 or 4 cytopenia, especially lymphopenia, in the absence of signs of infection is not interpreted as a DLT.

DLT will be defined as follows:

Version Date: 09/24/2021

Any grade 3 or 4 toxicity possibly, probably or definitely related to the rhIL-15 treatment that occurs during the first 6 weeks of treatment, with the following exceptions:

Hematologic exceptions:

- Grade 3 or 4 lymphopenia
 - o rhIL-15 will be continued in the event of asymptomatic grade 3 or 4 lymphopenia, unless there are clinical signs of significant infection (persistent fevers, labile blood pressure, localized complaints or findings on physical exam, hypoxia or organ dysfunction).
- Grade 3 neutropenia
 - o rhIL-15 will be continued in the event of grade 3 neutropenia unless there are clinical signs indicating a significant infection, as listed above.
- Grade 3 leukocytosis (WBC > 100,000/mm³) in the absence of signs of leukostasis or other toxicities possibly related to the expansion of activated cells.
- Grade 3 or 4 anemia that lasts for \leq 3 days and does not cause hypotension or organ dysfunction. If the anemia last for more than 3 days, it is considered a DLT.

Other exceptions:

• Any event that can clearly be determined to be unrelated to the treatment regimen.

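### Section 3.3, Table 1: the condition for returning alemtuzumab from 10 mg to 30 mg appears to carry a wrong sign or word, so that read literally a related grade 1 event blocks the return (minor)

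*Combined protocol and SAP*

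**What the plan says.** The table at issue is Table 1 of Section 3.3; the background section has another table with the same number. Its scope is given by its title: "Dose Modification of Alemtuzumab for non-hematologic toxicity related to alemtuzumab". The row for a first grade 3 event at 30 mg has two parts:

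- Immediate action: "Hold alemtuzumab until toxicity resolves to Grade ≤ 1 or baseline".
- Resumption: "Resume alemtuzumab at 10 mg tiw, increase to 30 mg tiw if and when no Grade ≤2 AEs".

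Other rules bear on the same decision:

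- The grade 1 and grade 2 rows, at any dose, require no action and state "No interruption".
- A first grade 3 event at 10 mg leads to a hold and a restart at 10 mg. A second stops the drug, as does any grade 4 event.
- The footnote on long holds reads: "If alemtuzumab is held >7 days, restart at 3 mg dose and titrate up as in the first week".
- Section 3.2 governs the first titration. The step from 3 mg to 10 mg is allowed with up to "grade 2 acute, infusion related toxicity and grade 1 or less skin rash". For the step from 10 mg to 30 mg it says only: "If this is well tolerated the dose on Day 3 and Day 5 should be 30 mg".

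**The concern.** A step-up rule normally names the toxicity that is too severe to allow an increase. This one names the mild grades as the bar and leaves the higher grades unmentioned, which is the usual pattern reversed. A patient correctly restarted at 10 mg with residual grade 1 toxicity fails the step-up test at once.

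This is an operative dosing instruction. A prescriber who follows the print keeps that patient at one third of the standard dose because of an event that the rest of the table disregards. A prescriber who takes it for a slip goes back to 30 mg. What is at stake is the alemtuzumab dose delivered after a first grade 3 event.

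**Working it through.** **Step 1: the rule, grade by grade.** The table shows the decision at 10 mg by the highest alemtuzumab-related non-hematologic grade present. It sets the printed rule beside the two plausible corrections: changing the sign (no grade 2 or higher) or dropping the 'no' (grade 2 or lower is acceptable).

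| Highest related grade | As printed | No grade 2 or higher | Nothing above grade 2 |
|---|---|---|---|
| 0 | step up | step up | step up |
| 1 | barred | step up | step up |
| 2 | barred | barred | step up |
| 3 | not named; other rows hold or stop | barred | barred |
| 4 | not named; other row stops | barred | barred |

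Both corrections let a patient with a related grade 1 event step up, and the print does not. They differ from each other only at grade 2.

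**Step 2: fit with neighbouring rules.** The first correction equals the restart threshold in the same row. The second matches the infusion-toxicity tolerance that Section 3.2 uses for its first step. The printed rule matches neither. Adjacent rows are also more lenient: a first grade 3 infection resumes directly at 30 mg, and so does a first grade 4 hematologic toxicity once it has resolved to grade 1 or baseline (Table 2). A patient held for more than 7 days is re-titrated under the first-week rules, while one held for a shorter time faces the stricter printed bar. Table 1 also has a row for a second grade 3 event at 30 mg, so return to 30 mg is expected.

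**Step 3: size.** The plan gives no figure to reproduce. Inputs, from Sections 3.1 and 3.3:

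- Planned total: 3 + 10 + 30 + 30 + 9 × 30 = 343 mg over 13 doses, of which 11 are 30 mg.
- r = doses remaining after the event: 10 if it follows the first 30 mg dose, down to 0 after the last.
- k = doses missed during the hold: 0 to 2, because resuming on the Monday/Wednesday/Friday schedule within 7 days of the event dose misses at most 2.
- Each dose given at 10 mg instead of 30 mg loses 20 mg.

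Assumptions: a related grade 1 event lasts through week 6; missed doses are not made up; the 11 possible event doses are weighted equally. Doses missed in the hold are lost under either rule and are not counted. The cell does not say how long 10 mg must be given before the increase, so both readings are shown:

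- One 10 mg dose first: loss = 20 × max(0, r − k − 1).
- One week (three doses) first: loss = 20 × max(0, r − k − 3).

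For k = 1, over r = 10 to 0:

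- One dose: 160, 140, 120, 100, 80, 60, 40, 20, 0, 0, 0. Median 60 mg; 60/343 = 17%.
- One week: 120, 100, 80, 60, 40, 20, 0, 0, 0, 0, 0. Median 20 mg; 20/343 = 6%.

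| Doses missed (k) | One dose first: range, median | One week first: range, median |
|---|---|---|
| 0 | 0–180 mg, 80 mg (23%) | 0–140 mg, 40 mg (12%) |
| 1 | 0–160 mg, 60 mg (17%) | 0–120 mg, 20 mg (6%) |
| 2 | 0–140 mg, 40 mg (12%) | 0–100 mg, 0 mg |

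If the event is present at only three doses after the first 10 mg dose, the loss is at most 60 mg on the one-dose reading and at most 20 mg on the one-week reading.

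For grade 1 these losses hold under either correction. For grade 2 the loss is zero against the first correction and the same as above against the second.

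**The case against.** The strongest defence is that the rule is deliberately strict. Restarting at 10 mg and tripling the dose after a grade 3 event are different decisions, and the second may reasonably need a cleaner patient. The wording makes the bar temporary. The grade 1 and 2 rows concern interruption, and staying at 10 mg is not an interruption. The grade tolerance in Section 3.2 applies to the 3 mg to 10 mg step; the 10 mg to 30 mg step has no stated grade to conflict with. Since other rows already deal with grades 3 and 4 at 10 mg, the cell could mean that no low-grade toxicity remains.

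Much of this stands. It rules out calling the row contradictory, and a strict intent cannot be fully excluded from the readable text. It does not make the print clear: a rule requiring no toxicity at all would more naturally say so without naming a grade, and it would be stricter than the adjacent rows.

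A reader might also infer that the cell lets a patient step up with grade 3 or 4 toxicity. The documents do not support that, because the other rows require a hold or a stop, so there is no safety gap there.

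Two practical objections also stand in part. Figure 10 covers this same titration and may state the threshold clearly. And the trial is at one institution whose team meets weekly during active treatment to discuss each patient (Section 7.4.1), which makes divergent dosing less likely, though it does not correct the text.

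**Conclusion.** The cell probably contains a wrong sign or word and should be clarified; the point is minor. It is an inconsistency of thresholds that affects alemtuzumab dose intensity after a first grade 3 event. Under the assumptions above, with one missed dose, the median loss is about 20 to 60 mg of 343 mg (6% to 17%).

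The documents give no frequency for reaching this row, but several rules divert patients from it:

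- All alemtuzumab dosing falls inside the DLT window, and a DLT is "Any grade 3 or 4 toxicity possibly, probably or definitely related to the rhIL-15 treatment that occurs during the first 6 weeks of treatment", subject to listed exceptions. A DLT leads to removal from therapy unless the investigator makes an exception (Section 3.6.1).
- Allergic (infusion) reactions of grade 3 or higher are removal criteria, and grade 3 infections have their own rows.
- Treatment-related grade 2 events lasting more than 14 days are a removal criterion, which limits how long grade 2 could block the increase.
- Infusion reactions tend to improve with later doses (Section 14.2.2), so a lasting block would have to come from other related events.

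A reader might take the 180 mg maximum (52% of the planned dose) as the typical cost. It is not: it needs the event at the first 30 mg dose, no missed dose, only one 10 mg dose before step-up, and a related grade 1 event through week 6. A reader might also infer that dose finding is affected. The DLT definition, the 3+3 rules and the sample size do not depend on this cell.

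**What to change.** First check the sign against the source document and Figure 10. Then replace the condition with an explicit threshold. Suggested default: *raise to 30 mg three times weekly once no alemtuzumab-related non-hematologic AE is Grade 2 or higher (that is, Grade 1 or below, or baseline)*. This matches the row's own restart criterion.

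If the sponsor means to tolerate grade 2, write instead *once no related AE is above Grade 2*. The choice between the two is clinical and matters only at grade 2. If a zero-toxicity rule is truly intended, say that plainly. It would help to state in the same cell whether one dose or one week at 10 mg must come first. Make Figure 10 match.

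The cost is one table cell, and the figure if it repeats the wording, by amendment. Nothing in the design or sample size changes.

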3.6 CRITERIA FOR REMOVAL FROM PROTOCOL THERAPY AND OFF STUDY CRITERIA

3.6.1 Criteria for removal from protocol therapy

Prior to removal from study, effort must be made to have all subjects complete a safety visit approximately 30 days following the last dose of study therapy. Criteria for removal from protocol therapy:

- Unacceptable adverse event(s), unless it is felt by the Principal Investigator to be in the patient's best interests to remain on study in exceptional circumstances, including:
 - o DLT as defined in Section 3.1.1
 - o Persistent (> 14 days) treatment-related grade 2 (non-DLT) adverse events
 - o Grade 3 or higher alemtuzumab allergic (infusion) reaction
 - o Third occurrence of alemtuzumab related grade 3 infection
 - o Third occurrence of alemtuzumab related grade 4 hematologic toxicity
 - o Any grade auto-immune cytopenia
 - o Grade ≥3 VTE during or within four weeks of protocol treatment while on appropriate VTE prophylaxis
- The detection of anti-IL-15 neutralizing antibody serum titer ≥ 500 ng/mL as described in **Appendix E** prior to subsequent treatment cycles.
- Evidence the patient has developed autoimmunity that involves a vital organ (heart, kidney, brain, eye, thyroid or adrenal gland, colon, lung). Patients who develop new auto-antibodies without clinical evidence of end-organ dysfunction will be seen by the appropriate internal medicine subspecialists to assess their risk for developing an autoimmune syndrome.
- Inability to receive all doses of rhIL-15 treatment during treatment weeks 1 and/or 2 for any reason.
- Positive pregnancy test
- Completion of protocol therapy including a 30-day safety visit
- Disease progression

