14.2 ALEMTUZUMAB (CAMPATH-1H)

Alemtuzumab causes the lysis of lymphocytes by fixing to CD52, a highly expressed, non-modulating antigen on the surface of lymphocytes. It mediates the lysis of lymphocytes via complement and antibody-dependent, cell-mediated cytotoxicity mechanisms.

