14.2.2 Toxicity

The majority of adverse events seen in trials have been administration related and of short duration. Serious adverse events, some of which were fatal, have been observed in association with treatment of alemtuzumab.

Please refer to the package insert for a complete listing of all toxicities.

Infusional reactions occur in most patients. They commonly consist of rigors, fever, headache, nausea, vomiting and diarrhea, rash, pruritus, dyspnea and hypotension. Acute infusional reaction may also include chills, abdominal and back pain, bronchospasm, angioedema, tachyarrhythmia etc. These reactions are most prominent during the first dose of alemtuzumab administration and improve with subsequent treatments. To reduce the frequency and severity of the first dose reaction, a step-up dose escalation schedule and proper premedication should be used.

Myelosuppression: anemia, neutropenia, thrombocytopenia, prolonged and profound lymphopenia.

Infections: common bacterial (pneumonia and sepsis) or opportunistic infections (e.g. Pneumocystis jiroveci pneumonia, oral candidiasis, herpes zoster, CMV reactivation, Cryptococcus).

Version Date: 09/24/2021

Reported adverse events by organ systems:

• **Body as a whole:** Allergic reaction, rigors, fever, chills, headache, back and abdominal pain, infection and fatigue.

- Cardiovascular: Hypertension, hypotension, tachycardia, atrial arrhythmia, ventricular tachycardia, angina, myocardial infarction and peripheral vasoconstriction.
- **Digestive:** Anorexia, nausea, vomiting, diarrhea, constipation, dyspepsia, liver function abnormality.
- **Hematological:** Neutropenia, lymphopenia, thrombocytopenia, anemia, DIC, hemolysis, eosinophil disorder, bleeding (GI, gum, ecchymosis).
- Musculoskeletal: Myalgia, arthritis, bone pain, hypotonia, tremor.
- Metabolic and Nutritional: Tumor lysis syndrome, acidosis.
- Nervous System: Dizziness, confusion, somnolence, peripheral neuropathy, cerebral hemorrhage, speech disorder, mental status changes, paresthesia, syncope, depression, aphasia.
- **Pulmonary:** Bronchospasm, cough, pleural effusion, pulmonary edema, interstitial pneumonitis.
- **Skin/Subcutaneous:** Angioedema, facial flushing, diaphoresis, pruritus, rash, urticaria, injection site reaction (subcutaneous route).
- **Urogenital:** Hematuria, oliguria, polyuria, urinary retention, urinary tract infection, impotence.
- **Aural:** Tinnitus, hearing loss.

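### Table 2's grade 4 hematologic hold on alemtuzumab does not exempt lymphopenia, the drug's expected effect, so a patient who reaches it from a higher baseline loses or delays part of the 13-dose course

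*Combined protocol and SAP*

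**What the plan says.** Table 2 in Section 3.3 governs alemtuzumab dosing for all hematologic toxicity attributed to alemtuzumab. Grades 1 to 3 cause no interruption. At a first or second grade 4 event the instruction is "Hold therapy until toxicity resolves to Grade ≤ 1 or baseline"; dosing resumes at 30 mg after the first and at 10 mg after the second, and a third ends alemtuzumab. The footnote adds: "If alemtuzumab is held >7 days, restart at 3 mg dose and titrate up as in the first week". The only cytopenia with its own row is autoimmune cytopenia.

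Section 3.6.1 repeats the last step as a reason for removal from therapy: "Third occurrence of alemtuzumab related grade 4 hematologic toxicity". That list carries a waiver, beginning "unless it is felt by the Principal Investigator to be in the" and continuing to the patient's best interests, for exceptional circumstances.

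The course itself is "for up to 13 doses in the absence of disease" progression or unacceptable toxicity, with the infusions placed in weeks 3 to 6 (Sections 3.1 and 3.2).

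On the drug's effect, Section 14.2 states: "Alemtuzumab causes the lysis of lymphocytes by fixing to CD52". Section 14.2.2 lists "Myelosuppression: anemia, neutropenia, thrombocytopenia, prolonged and profound lymphopenia". Section 3.1.1 exempts grade 3 or 4 lymphopenia from the rhIL-15 DLT definition and lets rhIL-15 continue through it when asymptomatic, with this contrast: "Unlike cytopenias noted in patients receiving cytotoxic chemotherapies or alemtuzumab treatment, these drops are usually transient".

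**The concern.** The exemption exists for the drug whose lymphopenia is brief and is missing for the drug whose lymphopenia is intended and long-lasting. Because Table 2 separates no lineage other than autoimmune cytopenia, and the protocol itself counts lymphopenia as a hematologic toxicity of alemtuzumab, a grade 4 lymphocyte count falls inside the hold rule.

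What is at stake is exposure to the combination during the period the trial uses to judge it. The first 6 weeks decide dose escalation (Section 3.1.2), and restaging comes at the end of week 6 (Section 3.4.2). A patient held for the drug's expected effect receives fewer alemtuzumab infusions before both, whether or not the missed doses are given later.

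**Working it through.** **Planned course.** Take Day 1 as Monday of week 1. Section 3.1 puts week 3 doses on Days 15, 16, 17 and 19 (3, 10, 30 and 30 mg), then 30 mg on Monday, Wednesday and Friday of weeks 4 to 6: Days 22, 24, 26, 29, 31, 33, 36, 38 and 40. That is 4 + 9 = 13 infusions, matching the protocol's figure. The total is 3 + 10 + 11 × 30 = 343 mg.

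**Would a grade 4 count be seen?** Section 3.4.1 schedules a CBC with differential three times a week (four in week 3), with a ±2 day window. A grade 4 count would be found during the course, though not necessarily on a dosing day.

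**Does the release to baseline help?** Only a patient who entered with an equally low count. Section 2.1.1.9 sets neutrophil and platelet floors but no lymphocyte limit, so such patients can enter. A patient still meeting the chronic ATL definition (absolute lymphocytosis, Section 1.2.1 and Appendix B) has no low baseline to return to.

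**Illustrative hold from Day 22.** Four infusions have been given: 3 + 10 + 30 + 30 = 73 mg; nine remain. Hold length is counted from the first withheld dose, so a 7-day hold does not trigger the 3 mg restart. Holds over 7 days restart on the week 3 pattern (3, 10, 30, 30 mg).

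| Hold | Infusions by Day 42 | mg by Day 42 (share of 343) | If made up to the 13-dose cap |
|---|---|---|---|
| 7 days, resume Day 29 | 4 + 6 = 10 | 73 + 6 × 30 = 253 (74%) | 343 mg (100%), last dose Day 47 |
| 14 days, restart Days 36, 37, 38, 40 | 4 + 4 = 8 | 73 + 73 = 146 (43%) | 73 + 73 + 5 × 30 = 296 mg (86%), Day 52 |
| 19-21 days, restart Monday Day 43 | 4 | 73 (21%) | 73 + 73 + 5 × 30 = 296 mg (86%), Day 59 |

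A hold longer than 21 days also leaves 4 infusions by Day 42. The 47 mg shortfall after make-up (343 − 296) is (30 − 3) + (30 − 10), because the repeated 3 and 10 mg doses use two of the 13. Make-up dosing restores most of the milligrams but does not change the count inside the window.

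**Other start days.** For holds starting on Day 17, 22, 29 or 36, infusions by Day 42 are:
- 3-day hold: 11, 11, 11, 11
- 7-day hold: 10, 10, 10, 10
- 14-day hold: 6, 8, 7, 10
- 21 days or more: 2, 4, 7, 10

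**How long might a hold last?** The earlier alemtuzumab trial in ATL reported a median of 1.8 months to an absolute lymphocyte count of at least 200/µL (Section 1.2.2.4), about 1.8 × 30.4 = 55 days. The alemtuzumab course here spans 40 − 15 + 1 = 26 days. This is only a guide: that trial gave up to 12 weeks of single-agent drug, and the start of the interval is not stated.

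**Third-occurrence stop.** It needs three grade 4 episodes with two intervening recoveries to grade 1 or baseline, all within 26 days. It would rarely be reached; the first hold is what matters.

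**The case against.** **Adverse-event definitions.** Section 3.6.1 frames its line as an unacceptable adverse event. Section 6.1.2.1 treats a laboratory abnormality as an adverse event only under listed conditions, and Section 8.1.1 describes an adverse event as unintended. Together these could support ignoring asymptomatic lymphopenia. But 6.1.2.1 governs recording, Table 2 does not cite it, and Section 14.2.2 lists lymphopenia as a toxicity. A site that skipped the hold on this basis would be supplying an exemption the text does not contain.

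**Prior rhIL-15.** Alemtuzumab starts on Day 15, when NK cells peaked in the earlier subcutaneous rhIL-15 trial (Section 1.2.4.5), and NK cells carry little CD52 (Section 1.2.2.3). Grade 4 lymphopenia may therefore be less common or shorter than with alemtuzumab alone. That stands, but it concerns frequency, not what the rule requires once grade 4 is reached.

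**Caution is defensible.** Five of 14 PTCL patients on alemtuzumab died of infectious complications (Section 1.2.3.2), and all patients in the earlier ATL trial developed CMV antigenemia (Section 1.2.2.4). A deliberate hold for profound lymphopenia is a position one could take. The protocol does not state it, and it sits badly with a fixed course of a lymphocyte-depleting antibody.

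**Investigator discretion.** The waiver in Section 3.6.1 covers removal from therapy in exceptional circumstances. It does not reach the Table 2 hold.

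**Conclusion.** The point holds conditionally. A patient who reaches grade 4 lymphopenia in weeks 3 to 6 without an equally low baseline must, under Table 2 as written, be held for alemtuzumab's expected effect and will lose or delay doses. The illustration of 10, 8 or 4 of 13 infusions inside the 6-week window rests on a chosen start (Day 22) and chosen hold lengths; it shows the rule's consequence and is not a forecast. It does not depend on the lymphocyte cut-off for grade 4, which the protocol text does not print.

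Three stronger readings are tempting and not supported:
- **That most patients will be affected.** I found no rate of grade 4 lymphopenia; Appendix G, which tabulates the earlier trial, was available to me only in part.
- **That the third-occurrence rule will remove patients.** Each episode must first resolve, in a 26-day course.
- **That held patients become inevaluable, or that the MTD determination fails.** Section 10 replaces patients without DLT who do not finish 6 weeks of therapy, but the text does not say whether a held patient has finished. All rhIL-15 is given before alemtuzumab starts, and DLT is defined by relation to rhIL-15.

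Silence on make-up doses is missing detail and not part of this point. What remains is a stated rule that works against the planned course and is cheap to correct.

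**What to change.** Add to Table 2, and for consistency to the matching line in Section 3.6.1: *Lymphopenia, or a fall in total WBC explained by it, does not trigger the hold, the 3 mg restart or the third-occurrence stop unless clinical signs of significant infection listed in Section 3.1.1 are present.* Leave the rule unchanged for neutropenia, thrombocytopenia, anemia and autoimmune cytopenia, and keep Table 1's hold for grade 3 infection.

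A patient whose only grade 4 hematologic event is such lymphopenia would then keep all 13 infusions by Day 40, absent another reason to hold. The cost is a short amendment, with no added tests or patients.

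The real downside is dosing through profound lymphopenia with its infection risk. During treatment this is mitigated by the PJP and herpes prophylaxis in Section 4.3 and the weekly CMV PCR in Section 3.4.1. Table 1's hold acts only once an infection has occurred, and the CD4 monitoring in Section 3.4.5 begins only in follow-up. If the sponsor does intend to hold for lymphopenia, Table 2 should say so explicitly.
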